5.4.2.2. Continuous Endpoints

5.4.2.2.1. HBsAg, HBeAg, HBV DNA and ALT

Descriptive statistics on actual values [original unit and \log_{10} transformed values (except for ALT)], changes from baseline and changes from RT over time in HBsAg, HBeAg, HBV DNA and ALT will be summarized. Mean (+/- SE) plots of the values, change from baseline and change from RT over time will be presented by analysis phase. The change from baseline value to nadir (i.e. maximum decrease for each participant) in HBsAg, HBeAg and HBV DNA will be summarized descriptively. Box plots of the changes to nadir in HBsAg, HBeAg, and HBV DNA will display the distribution.

Change from baseline based on \log_{10} transform for quantitative HBsAg and HBeAg will be analyzed using mixed effects model for repeated measures [MMRM]) including analysis time point (week), baseline blood marker variable, and their interaction. The covariance structure will include a random intercept at the level of the participant to capture between-participant variability, while within-participant variability will be captured with an unstructured (type=UN) covariance matrix. In case of convergence problems, simpler variance-covariance structures such as Toeplitz or AR (1) will be considered. The selection of any of these structures will be determined after exploration of the observed correlation structure. The LS mean of change from baseline, standard error (SE), 90% confidence interval (CI) will be provided.

Descriptive statistics on actual values (original unit and \log_{10} transformed values) and changes from baseline (\log_{10} transformed values) at the end of treatment in HBsAg, HBeAg, HBV DNA and ALT (original unit) will be summarized by outcome response (i.e. by achieving a reduction of at least 2 \log_{10} IU/mL in HBsAg levels from baseline to Week 24, by NA treatment completion criteria status), by HBsAg seroclearance at the end of treatment period 2, FU Week 24 and FU Week 48, and by partial cure status at FU Week 24 and FU Week 48, and for participants who achieved functional cure at FU Week 24 and FU Week 48 if there is at least 10% response for each by-group.

Spaghetti plots for both absolute values and changes from baseline of HBsAg and HBV DNA will be presented over time per blood marker by selected subgroups (Section 5.7.5.1).

Waterfall plots for changes from baseline of HBsAg and HBeAg will be presented over time.

Descriptive statistics of the absolute values and changes from baseline over time in ALT will be summarized by analysis phase for those participants who had ALT elevation at baseline.

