 - qq. *Visits at follow-up Week 16, 20, 28, 32, 40, and 44 are optional for participants who continue NA treatment and for participants who have restarted NA treatment during the follow-up period, provided that their HBV DNA and ALT values are stable.*
 - rr. Liver function tests only.
 - ss. Urine pregnancy tests will be provided to the participants for at home use as necessary to ensure urine pregnancy tests are performed at least every 4 weeks. Participants will report the results to the study site personnel at the next visit, and these will be added to the source documents. If positive, the participant should contact the site immediately.
 - tt. No JNJ-3989/PegIFN- α 2a will be administered or dispensed during follow-up. Administration/Dispensation of NA is only applicable for participants who could not stop NA treatment, or for those who met the NA re-treatment criteria. In between study visits, participants will take NA at home and they will bring their NA treatment with them to each study visit.
 - uu. If the NA treatment completion criteria are met at Week 24, treatment with NA will be stopped at FU Week 2.
 - vv. Available historical data on HBeAg status before start of NA treatment will be collected in the CRF.
 - ww. A urinalysis and urine chemistry sample will be taken at FU Week 2. In case of abnormalities, the tests should be repeated at the following visits.
 - xx. Includes close monitoring for neuropsychiatric adverse events during the PegIFN- α 2a treatment period. Participants who develop a neuropsychiatric adverse event during PegIFN- α 2a treatment, will be monitored closely until the neuropsychiatric adverse event resolves, with frequent (at least weekly) follow-up phone calls.
 - yy. NA treatment should be re-started in accordance with the NA re-treatment criteria (see Section 6.7.1, NA Re-treatment Criteria and Monitoring After Stopping of NA and Section 10.12 Appendix 12, for guidance after stopping NA treatment).
 - zz. Participants enrolled before Protocol Amendment 3 was in effect, may have received JNJ-6379 as part of their study intervention.

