1.2. Study Design

This is a Phase 2a, open-label, single-arm, multicenter study to assess efficacy, safety, tolerability and pharmacokinetics of treatment with JNJ-3989, JNJ-6379 (as applicable), NA, and PegIFN- α 2a in virologically suppressed patients with chronic hepatitis B virus infection. Prior to Protocol Amendment 3, the study intervention also included JNJ-6379. Note that as of Protocol Amendment 3, JNJ-6379 has been removed as study intervention and the study will continue with JNJ-3989, NA and PegIFN- α 2a only. Participants had to stop JNJ-6379 treatment immediately after the implementation of Urgent Safety Measure (USM) and approval of the protocol amendment 3.

Approximately 50 virologically suppressed CHB-infected participants, 18-65 years (inclusive) of age, will be enrolled in this study. Approximately 40% HBeAg-positive participants will be enrolled.

[figure not shown]
The study will be conducted in 4 periods:

- Screening period (4 weeks [if necessary, can be extended to a maximum of 8 weeks decided on a case-by-case basis and in agreement with the sponsor]).
- Treatment Period 1 (12 weeks) consisting of combination treatment with JNJ-3989 + NA.
- Treatment Period 2 (12 weeks) adding PegIFN- α 2a to the combination treatment regimen of Treatment Period 1.
- Follow-up (FU) Period (48 weeks).

The total duration of individual participation will be up to 76 weeks (including 4 weeks of screening).

A schematic of the trial prior to Protocol Amendment 3 is presented in [Figure 1](#).

Figure 1: Schematic Overview of the Study – Prior to Protocol Amendment 3

[figure not shown]

ALT: alanine aminotransferase; DNA: deoxyribonucleic acid; EOS: end of study; EOSI: end of study intervention; FU: follow-up; HBeAg: hepatitis B e antigen; HBsAg: hepatitis B surface antigen; HBV: hepatitis B virus; JNJ-3989: JNJ-73763989; JNJ-6379: JNJ-56136379; LLOQ: lower limit of quantification; n: number of participants; NA: nucleos(t)ide analog; PegIFN-α2a: pegylated interferon alpha-2a; ULN: upper limit of normal; Q4W: every 4 weeks; QD: once daily; QW: once weekly.

^a. If NA treatment completion criteria (HBsAg <10 IU/mL, and HBeAg-negative, and HBV DNA <LLOQ, and ALT <3x ULN) have been met at Week 24, NA will be stopped at the next scheduled visit (ie, FU Week 2), otherwise NA treatment will continue during the complete FU period.

A schematic of the trial as of Protocol Amendment 3 is presented in [Figure 2](#).

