5.1.7. Level of Significance

Due to exploratory nature of this study, no formal test will be performed. Only two-sided 90% CIs will be provided with no adjustment for multiplicity.

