5.4.1.2. Continuous Endpoints

5.4.1.2.1. HBsAg, HBeAg, HBV DNA and ALT

Actual values (original unit and \log_{10} transformed values), changes from baseline (\log_{10} transformed values) and changes from RT (\log_{10} transformed values) over time in HBsAg, HBeAg, HBV DNA and ALT (actual values only) will be evaluated.

Change from baseline is defined as the value at a given time point minus baseline value.

The change from baseline value to the nadir (i.e. maximum decrease for each participant) in HBsAg, HBeAg, and HBV DNA will be evaluated at five intervals: treatment period 1 nadir (first 12 weeks of treatment), treatment period 2 nadir (second 12 weeks of treatment), on-treatment nadir (first 24 weeks), during follow-up nadir, and entire study nadir.

Only HBeAg positive participants will be used for the analysis of HBeAg values and changes from baseline.

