5.4.2. Analysis Methods

All secondary endpoints will be analyzed using the FAS. The analysis may be repeated in the IFN-FAS and modified FAS/IFN-FAS analysis sets if there is a difference of at least 2 participants between analysis sets.

Some analysis will be performed by group, as defined in Section 5.1.10. Summaries and graphs will be provided for each analysis phase, unless specified otherwise.

All secondary endpoints will be analyzed based on the observed case data. Additional analyses with specific imputation methods for missing data are added for selected endpoints.

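### The repeated-measures model for HBsAg and HBeAg is over-specified, its named fallbacks assume constant variance, and observed-case summaries at six optional follow-up visits can be shifted towards participants who stopped NA

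*SAP*

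**What the plan says.** SAP 5.4.2.2.1 models log10 change from baseline in HBsAg and HBeAg on visit, baseline value and their interaction, and reports LS means with 90% CIs. On the covariance it says: "The covariance structure will include a random intercept at the level of the participant to capture between-participant variability". In the same sentence it assigns within-participant variability to an unstructured (UN) matrix. If the fit does not converge, "simpler variance-covariance structures such as Toeplitz or AR (1) will be considered", with the choice made after the observed correlations have been inspected. The visits that enter the model are not listed. SAP 5.1.3 adds EOT1, EOT2 and EOS to over-time analyses by default, and these duplicate scheduled visits.

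For HBeAg, SAP 5.4.1.2.1 restricts the data: "Only HBeAg positive participants will be used for the analysis of HBeAg values and changes from baseline". SAP 1.2 plans about 50 participants and states: "Approximately 40% HBeAg-positive participants will be enrolled".

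On attendance, six follow-up visits (FU Weeks 16, 20, 28, 32, 40 and 44) carry a footnote in the Protocol 1.3 Schedule of Activities, which says that they "are optional for participants who continue NA treatment and for participants who have restarted NA treatment during the follow-up period". The option applies only while HBV DNA and ALT are stable. SAP 5.4.2 adds: "All secondary endpoints will be analyzed based on the observed case data".

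**The concern.** There are two separate issues.

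The first is the covariance. An unstructured matrix already contains any between-participant component, so a random intercept beside it cannot be estimated. With many visits and few participants the unstructured matrix may itself fail, and the fallback then becomes the analysis in practice. Toeplitz and AR(1) in standard form give every visit the same variance. If the spread of log10 change grows over time, the CIs are too wide early and too narrow late. Late follow-up is where durability is judged.

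The second is who is measured. NA is stopped only if Week 24 criteria are met, and these include HBsAg below 10 IU/mL. Participants off NA must attend the six visits, while stable participants on NA may skip them. Attendance is therefore tied to the outcome, and an observed-case mean or proportion at those visits may describe a different group from the one at neighbouring visits.

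**Working it through.** **The plan's own precision figure.** The only one is the Clopper-Pearson interval in SAP 3. For 25/50 it gives 0.376-0.624, width 0.248, and this reproduces. It concerns the primary responder proportion. The documents give no precision figure for the repeated-measures model.

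**Visits.** The quantitative HBsAg and HBeAg rows of the Schedule of Activities give 20 post-baseline samples: Weeks 4, 8, 12, 14, 16, 20, 24 (7) and FU Weeks 2, 4, 8, 12, 16, 20, 24, 28, 32, 36, 40, 44, 48 (13). There is none at Week 2.

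**Parameter count.** An unstructured matrix over T visits has T(T+1)/2 parameters.
- T = 20: 20 × 21/2 = 210. The random intercept makes 211.
- T = 23, with EOT1, EOT2 and EOS: 23 × 24/2 = 276.

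**Redundancy.** If V = s²J + R with R unstructured, any s² that leaves R positive definite gives the same V. On simulated data (N = 50), s² = 0, 0.021, 0.041 and 0.074 all gave log-likelihood 944.3275 and a FU Week 48 SE of 0.127. The split is arbitrary, but the LS means and SEs are the same. The intercept is also redundant with a full Toeplitz matrix; it is identifiable with AR(1).

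**Can the unstructured matrix be estimated over 20 visits?** Each visit has its own intercept and baseline slope.
- HBeAg: 40% of 50 is about 20 participants. 20 - 2 = 18 residual df, below 20, so the matrix is singular.
- HBsAg: 50 - 2 = 48, above 20, so it is estimable with near-complete data. With the 14 mandatory visits ordered first, the last optional visit needs 19 + 2 = 21 coefficients. At least 22 participants must then attend all six optional visits. If 32% stop NA (assumed; 16 of 50), at least 22 - 16 = 6 NA-continuers must do so.

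**Constant-variance fallback.** The documents give no SDs, so these are assumed, interpolated linearly between Weeks 4, 24 and 72 (FU Week 48). With r = pooled SD / true SD at the visit, coverage is about 2Φ(1.645r) - 1.

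| SD at Week 4 / Week 24 / FU Week 48 | Pooled SD | r | Coverage of nominal 90% CI |
|---|---|---|---|
| 0.3 / 0.6 / 0.9 | 0.668 | 2.23 / 1.11 / 0.74 | about 100% / 93% / 78% |
| 0.4 / 0.6 / 0.7 | 0.604 | 1.51 / 1.01 / 0.86 | 99% / 90% / 84% |
| 0.5 / 0.6 / 0.6 | 0.583 | 1.17 / 0.97 / 0.97 | 95% / 89% / 89% |

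**Optional visits.** With 32% stoppers and a fraction q of the others attending, stoppers make up 0.32/(0.32 + 0.68q) of those seen: 100% at q = 0, 65% at 0.25, 48% at 0.5 and 32% at 1. They are the majority only if q is below 0.32/0.68 = 0.47.

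A simulation used N = 50, 250 runs, SDs 0.3/0.6/0.9, and attendance driven by Week 24 HBsAg below 10 IU/mL:

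| Attendance of NA-continuers | Observed-case bias, FU Week 16 / 44 (log10) | Model bias | Model 90% CI coverage, FU Week 48 |
|---|---|---|---|
| 0% | -0.41 / -0.34 | 0.01 or less | 79% |
| 50% | -0.08 / -0.07 | 0.01 or less | 79% |
| 100% | 0 / 0 | 0.01 or less | 79% |

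The model here was random intercept + AR(1). Its coverage does not move with attendance, so the CI error comes from the variance assumption. A shorter set of runs with SDs 0.4/0.6/0.7 showed model deviations of up to 0.04. At FU Week 48, where no data were missing, the deviation was -0.03, so this looks like simulation noise.

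**The case against.** A reader might infer that the model cannot be fitted and that the over-time means and CIs will be wrong. The documents do not support that. The redundant intercept changes no LS mean or SE, the HBsAg matrix is estimable with near-complete data, and the SAP has a convergence fallback. Its wording gives Toeplitz and AR(1) as examples, so heterogeneous versions are permitted, though not required.

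The single 20-visit model is also a reading, because the visits are not listed. SAP 5.4.2 plans summaries and graphs by analysis phase. Fitted by phase, follow-up has 13 visits and 13 × 14/2 = 91 parameters, and 18 residual df would suffice for HBeAg with complete data. That stands. It does not settle the matter: the last optional visit would still need 12 + 2 = 14 coefficients, hence 15 of about 20 participants attending all six. In this subgroup, stopping NA also requires being HBeAg-negative at Week 24, so many may be free to skip those visits.

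A reader might also infer that the six visits are attended mainly by NA-stoppers and that this biases the model. The documents give no attendance rate, and participants on NA with unstable values must still attend. The model includes Week 24 HBsAg, so attendance that follows it is largely missing at random. HBeAg, HBV DNA and ALT also decide NA status and are not in the HBsAg model, so some residual bias is possible.

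The main off-treatment results are well placed. Off-treatment seroclearance is emphasised at FU Weeks 12, 24, 36 and 48, functional and partial cure use only those weeks, and none is optional. SAP 5.4.2.1.3.2 adds a summary restricted to participants off all treatment. Summaries report n, and spaghetti plots show every measurement.

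Finally, the coverage figures rest on assumed SDs. Growing spread is plausible, since Protocol 4.3.1 describes late HBsAg in the Phase 1/2a study as ranging from near baseline to more than 1 log10 below it. It is not established.

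**Conclusion.** The point holds in limited form. The random intercept is an error to delete, not a source of bias. If all 20 visits enter one model, the unstructured matrix is singular for HBeAg and may fail for HBsAg, so the fallback is likely to be used. Standard Toeplitz or AR(1) then gives about 78-84% coverage at FU Week 48 if the SD rises from 0.3-0.4 to 0.7-0.9, and about 89% if it is nearly constant.

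Separately, observed-case means at the six optional visits can shift by about -0.4 log10 if no NA-continuer attends, by about -0.08 at 50% attendance, and not at all at full attendance. Observed-case proportions there are open to the same selection.

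All of these sizes depend on assumed SDs, correlations, mean trajectory, stopper share and attendance. The repeated-measures model is largely protected from the attendance effect. The primary endpoint, a Week 24 proportion with an exact CI, is unaffected. The study makes no formal test: "Only two-sided 90% CIs will be provided with no adjustment for multiplicity". The harm is to the description of HBsAg and HBeAg over time, which is a stated secondary endpoint.

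**What to change.** In SAP 5.4.2.2.1:
- Delete the random intercept.
- List the model visits and exclude EOT1, EOT2 and EOS.
- Fit the unstructured matrix with Kenward-Roger df on a reduced set, for example Weeks 4, 8, 12, 16, 20, 24 and FU Weeks 12, 24, 36, 48: 10 × 11/2 = 55 parameters.
- Fix the fallback order before the data are inspected: heterogeneous Toeplitz, then ARH(1).
- For HBeAg, start at ARH(1) with small-sample-corrected SEs. Plain empirical SEs tend to be too small with about 20 participants.

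For the descriptive tables and plots, show the six optional visits by NA status with n, and not as all-participant values.

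The cost is SAP wording and programming, and fewer visits in the all-participant model and displays. The example set also leaves out Week 14 and FU Weeks 2, 4 and 8, which are not optional; these can stay in the descriptive summaries.

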5.4.2.3. Time to Event Endpoints

The Kaplan-Meier method will be used to estimate and plot the cumulative incidence and estimate the median time with 90% CI. In addition, the number and percentage of participants who had an event or were censored will be reported.

5.5. Exploratory Endpoints

See Section 1.1 for a list of the exploratory endpoints. All exploratory endpoints will be analyzed using observed case data.

5.5.1. Definitions

5.5.1.1. Binary Endpoints

5.5.1.1.1. Liver Stiffness Measurement

The following liver stiffness measurements (LSM) changes from baseline (in terms of reductions) will be evaluated over time at Week 24, FU Week 24 and FU Week 48:

- ≥ 1 kPa
- ≥ 2 kPa
- ≥ 4 kPa
- ≥ 6 kPa

Only participants from sites with available VCTE (Fibroscan) will be included in the analysis. Within these participants, missing LSM (in kPa) at a specific timepoint will be considered as non-responders for that timepoint. No imputation rule will be used in case of missing data.

5.5.1.1.2. HBV RNA Cut-offs

The cut-offs for HBV RNA are as follows:

- $< \text{LOD}$
- $< \text{LLOQ}$
- < 1000 copies/mL

The cut-offs for HBV RNA change from baseline and RT are as follows:

- decrease by ≥ 1.0 log copies/mL
- decrease by ≥ 2.0 log copies/mL
- decrease by ≥ 3.0 log copies/mL

5.5.1.1.3. HBcrAg Cut-offs

The cut-offs for HBcrAg are as follows:

- < 3.0 log U/mL
- < 4.0 log U/mL

The cut-offs for HBcrAg change from baseline and RT are as follows:

- decrease by ≥ 1.0 log U/mL
- decrease by ≥ 2.0 log U/mL

- decrease by $\geq 3.0 \log U/mL$

5.5.1.1.4. Anti-HBe Antibodies

Participants who have positive and negative anti-HBe values will be evaluated over time.

5.5.1.2. Continuous Endpoints

5.5.1.2.1. Liver Stiffness Measurement

Severity of liver disease at the end of study intervention and follow-up versus baseline will be evaluated by the changes in fibrosis over time according to Fibroscan LSM.

Change from baseline is defined as the value at a given time point minus baseline value.

5.5.1.2.2. HBV RNA and HBcrAg

Actual values, changes from baseline (log transformed value) and changes from RT over time in HBV RNA and HBcrAg will be evaluated.

Change from baseline is defined as the value at a given time point minus baseline value.

The change from baseline value to nadir (i.e. maximum decrease for each participant) in HBV RNA and HBcrAg will be evaluated at five intervals: treatment period 1 nadir (first 12 weeks of treatment), treatment period 2 nadir (second 12 weeks of treatment), on-treatment nadir (first 24 weeks), during follow-up nadir, and entire study nadir.

5.5.1.2.3. Anti-HBs Antibodies

Actual values and change from baseline will be evaluated over time when anti-HBs antibodies are assessed.

Change from baseline is defined as the value at a given time point minus baseline value.

5.5.1.3. Time to Event Endpoints

5.5.1.3.1. Time to First HBV RNA<LOD

Time to first HBV RNA<LOD is defined as the duration from the date of first study intervention intake to the date of the first occurrence of HBV RNA<LOD (i.e. the date of the first occurrence of HBV RNA<LOD – the date of first study intervention intake + 1). The participants who did not achieve undetectability or who early withdrew from the study before achieving HBV RNA<LOD will be censored at the last HBV RNA assessment before the date of withdrawal.

Time to first HBV RNA<LOD will be also analyzed considering the participants who were retreated with NA before achieving HBV RNA<LOD as censored at the date of NA retreatment.

Only the participants with HBV RNA values $\geq LOD + 0.5 \log_{10} \text{ cp/mL}$ (i.e. $\geq 1.898 \log_{10} \text{ cp/mL}$) at baseline will be included in this analysis. Similarly, additional analyses for participants with HBV

RNA values $\geq \text{LOD} + 1.0 \log_{10}$ cp/mL and $\geq \text{LOD} + 2.0 \log_{10}$ cp/mL, respectively, will be summarized.

5.5.1.3.2. Time to First HBcrAg Undetectability

Time to first undetectability of HBcrAg is defined as the duration from the date of first study intervention intake to the date of the first occurrence of undetectability of HbcrAg (i.e. the date of the first occurrence of $\text{HBcrAg} < \text{LLOQ}$ – the date of first study intervention intake + 1). The participants who did not achieve undetectability or who early withdrew from the study before achieving undetectability of HBcrAg will be censored at the last HBcrAg assessment before the date of withdrawal.

Time to first undetectability of HBcrAg will be also analyzed considering the participants who were retreated with NA before achieving $\text{HBcrAg} < \text{LLOQ}$ as censored at the date of NA retreatment.

Only the participants with HBcrAg values $\geq \text{LOD} + 0.5 \log_{10}$ cp/mL (i.e. $\geq 3.5 \log_{10}$ U/mL) at baseline will be included in this analysis.

5.5.1.3.3. Time to Appearance of Anti-HBs Antibodies

Appearance of anti-HBs antibodies is defined as a baseline anti-HBs (quantitative) $< \text{LLOQ}$ and a post-baseline assessment $\geq \text{LLOQ}$.

Time to appearance of anti-HBs antibodies is defined as the time (days) from the date of first study intervention intake to the date of the first occurrence of anti-HBs antibodies appearance + 1. The participants who did not experience emergence of antibodies or who early withdrew from the study before showing emergence of anti-HBs antibodies will be censored at the last anti-HBs antibodies assessment before the date of withdrawal.

Time to appearance of anti-HBs antibodies will be also analyzed considering the participants who were retreated with NA before achieving appearance of anti-HBs antibodies as censored at the date of NA retreatment.

